## **7.2      Serious adverse events**

### **7.2.1    Definition of SAE**

An SAE is defined as any adverse event (appearance of (or worsening of any pre-existing) undesirable sign(s), symptom(s) or medical conditions(s) which meets any one of the following criteria:

- is fatal or life-threatening
- results in persistent or significant disability/incapacity
- constitutes a congenital anomaly/birth defect
- requires inpatient hospitalization or prolongation of existing hospitalization, unless hospitalization is for:

- routine treatment or monitoring of the studied indication, not associated with any deterioration in condition
- elective or pre-planned treatment for a pre-existing condition that is unrelated to the indication under study and has not worsened since signing the informed consent
- treatment on an emergency outpatient basis for an event not fulfilling any of the definitions of a SAE given above and not resulting in hospital admission
- social reasons and respite care in the absence of any deterioration in the patient's general condition
- is medically significant, i.e. defined as an event that jeopardizes the patient or may require medical or surgical intervention to prevent one of the outcome listed above e.g. may require treatment on an emergency outpatient basis for an event not fulfilling any of the SAE definition criteria and not resulting in hospitalization.

All malignant neoplasms will be assessed as serious under "medically significant" if other seriousness criteria are not met.

Any suspected transmission via a medicinal product of an infectious agent is also considered a serious adverse reaction.

All AEs (serious and non-serious) are captured on the eCRF, SAEs also require individual reporting to Novartis Drug Safety & Epidemiology department (DS&E) as per [section 7.2.2](#).

### **7.2.2 SAE reporting**

Each Serious Adverse Event (SAE), regardless of suspected causality, occurring after the patient has provided informed consent and until 30 days after the patient has stopped study participation (defined as time of last dose of drug taken or last visit whichever is later) will be reported by the investigator to Novartis DS&E by FAX within 24 hours of learning of its occurrence, even if it is not felt to be treatment-related.

Information about all SAEs is collected and recorded on the Serious Adverse Event Report Form. The principle investigator must assess the relationship of any SAE to the drug, complete the SAE Report Form, and send the completed, signed form by fax within 24 hours to Novartis Drug Safety and Epidemiology Department. In case of emergency, investigator other than principle investigator or staff can act for it instead of the principle investigator. The telephone and telecopy number of the contact persons in the local department of Clinical -Drug Safety and Epidemiology, specific to the site, are listed in the investigator folder provided to each site. The principle investigator must submit to Novartis monitor the original SAE report. The original copy of the SAE Report Form and the fax confirmation sheet must be kept with the case report form documentation at the study site.

Any SAEs experienced after this 30 day period should only be reported to Novartis DS&E by FAX if the investigator suspects a causal relationship to the drug.

Recurrent episodes, complications, or progression of the initial SAE must be reported as follow-up to the original episode, regardless of when the event occurs. This report must be submitted within 24 hours of the investigator receiving the follow-up information by the principle investigator. An SAE that is considered completely unrelated to a previously reported one should be reported separately as a new event.

Follow-up information is sent to the same person to whom the original SAE Report Form was sent, using a new SAE Report Form stating that this is a follow-up to the previously reported SAE and giving the date of the original report by FAX. The follow-up information should describe whether the event has resolved or continues, if and how it was treated, and whether the patient continued or withdrew from study participation.

If the SAE is thought to be related to the drug, a Drug Safety and Epidemiology Department associate may urgently require further information from the investigator for Health Authority reporting. Novartis may need to issue an individual safety report and others to inform all investigators involved in any study with the same drug that this SAE has been reported. Suspected Unexpected Serious Adverse Reactions (SUSARs) will be collected and reported to the competent authorities and relevant ethics committees in accordance with Directive 2001/20/EC or as per national regulatory requirements in participating countries.

### **7.3 Liver safety monitoring**

To ensure patient safety and enhance reliability in determining the hepatotoxic potential of the drug, a standardized process for identification, monitoring and evaluation of liver events has to be followed.

The following two categories of abnormalities / adverse events have to be considered during the course of the study (irrespective of whether classified/reported as (S)AE):

- Liver laboratory triggers, which will require repeated assessments of the abnormal laboratory parameter
- Liver events, which will require close observation, follow-up monitoring and completion of the standard base liver CRF pages

Please refer to [Table 14-1 in Appendix 2](#) for complete definitions of liver laboratory triggers and liver events.

Every liver laboratory trigger or liver event as defined in [Table 14-1 of Appendix 2](#) should be followed up by the investigator or designated personal at the trial site as summarized below. Detailed information is outlined in [Table 14-2 in Appendix 2](#).

For the liver laboratory trigger:

- Repeating the liver function test (LFT) to confirm elevation as appropriate.

Repeat laboratory tests must be entered on the appropriate unscheduled local laboratory CRF page.

- If the elevation is confirmed, close observation of the patient will be initiated, including consideration of treatment interruption if deemed appropriate.

For the liver events:

- Repeating the LFT to confirm elevation as appropriate
- Discontinuation of the drug if appropriate
- Hospitalization of the patient if appropriate
- A causality assessment of the liver event via exclusion of alternative causes (e.g., disease, co-medications)

- An investigation of the liver event which needs to be followed until resolution.

These investigations can include serology tests, imaging and pathology assessments, hepatologist's consultancy, based on investigator's discretion. All follow-up information, and the procedures performed must be recorded on appropriate CRF pages, including the liver event overview CRF pages.

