#### Laboratory items

Hematology;

Erythrocyte count, leukocyte count, hemoglobin, hematocrit, platelet count.

Blood chemistry;

Total protein, uric acid, ALP, AST, ALT, LDH, cholinesterase, BUN, creatinine, Na, K, Cl, total cholesterol, triglycerides, CPK, albumin, Ca, P, total bilirubin, amylase.

Urinalysis

Glucose, protein, occult blood.

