**Table 14-2 Follow Up Requirements for Liver Events and Laboratory Triggers**

| Criteria                      | Actions required  | Follow-up monitoring  |
|--------------------------------------|--|--|
| Potential Hy's Law case a | 
 
• Discontinue the study treatment immediately
 
• Hospitalize, if clinically appropriate
 
• Establish causality
 
• Complete liver CRF
 
   | ALT, AST, TBL, Alb, PT/INR, ALP and γGT until resolution c (frequency at investigator discretion) |
| ALT or AST                    |  |  |
| > 8 × ULN                            | 
 
• Discontinue the study treatment immediately
 
• Hospitalize if clinically appropriate
 
• Establish causality
 
• Complete liver CRF
 
  | ALT, AST, TBL, Alb, PT/INR, ALP and γGT until resolution c (frequency at investigator discretion) |
| > 3 × ULN and INR > 1.5              | 
 
• Discontinue the study treatment immediately
 
• Hospitalize, if clinically appropriate
 
• Establish causality
 
• Complete liver CRF
 
   | ALT, AST, TBL, Alb, PT/INR, ALP and γGT until resolution c (frequency at investigator discretion) |
| > 5 to ≤ 8 × ULN                     | 
 
• Repeat LFT within 48 hours
 
• If elevation persists, continue follow-up monitoring
 
• If elevation persists for more than 2 weeks, discontinue the study drug
 
• Establish causality
 
 | ALT, AST, TBL, Alb, PT/INR, ALP and γGT until resolution c (frequency at investigator discretion) |

| Criteria   | Actions required  | Follow-up monitoring   |
|--|---|--|
| > 3 × ULN accompanied by symptoms b       | 
 
Complete liver CRF
 
Discontinue the study treatment immediately
 
Hospitalize if clinically appropriate
 
Establish causality
 
Complete liver CRF
 
                           | ALT, AST, TBL, Alb, PT/INR, ALP and γGT until resolution c (frequency at investigator discretion)   |

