| > 3 to ≤ 5 × ULN (patient is asymptomatic)           | 
 
Repeat LFT within the next week
 
If elevation is confirmed, initiate close observation of the patient
 
   | Investigator discretion
Monitor LFT within 1 to 4 weeks   |
| ALP (isolated)                                |   |  |
| > 2 × ULN (in the absence of known bone pathology)   | 
 
Repeat LFT within 48 hours
 
If elevation persists, establish causality
 
Complete liver CRF
 
  | Investigator discretion
Monitor LFT within 1 to 4 weeks or at next visit  |
| TBL (isolated)                                |   |  |
| > 2 × ULN (in the absence of known Gilbert syndrome) | 
 
Repeat LFT within 48 hours
 
If elevation persists, discontinue the study drug immediately
 
Hospitalize if clinically appropriate
 
Establish causality
 
Complete liver CRF
 
 | ALT, AST, TBL, Alb, PT/INR, ALP and γGT until resolution c (frequency at investigator discretion)
Test for hemolysis (e.g., reticulocytes, haptoglobin, unconjugated [indirect] bilirubin) |
| > 1.5 to ≤ 2 × ULN (patient is asymptomatic)         | 
 
Repeat LFT within the next week
 
If elevation is confirmed, initiate close observation of the patient
 
   | Investigator discretion
Monitor LFT within 1 to 4 weeks or at next visit  |
| Jaundice   | 
 
Discontinue the study treatment immediately
 
Hospitalize the patient
 
Establish causality
 
Complete liver CRF
 
   | ALT, AST, TBL, Alb, PT/INR, ALP and γGT until resolution c (frequency at investigator discretion)   |
| Any AE potentially indicative of a liver toxicity*   | 
 
Consider study treatment interruption or discontinuation
 
Hospitalization if clinically appropriate
 
Establish causality
 
Complete liver CRF
 
                                      | Investigator discretion  |

a Elevated ALT/AST > 3 × ULN and TBL > 2 × ULN but without notable increase in ALP to > 2 × ULN

b (General) malaise, fatigue, abdominal pain, nausea, or vomiting, or rash with eosinophilia

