2.7 Other safety data

2.7.1 Laboratory data

Laboratory measurements will include Hematology (Erythrocyte count, leukocyte count, hemoglobin, hematocrit, platelet count); Blood chemistry (Total protein, uric acid, ALP, AST, ALT, LDH, cholinesterase, blood urea nitrogen, creatinine, Na, K, Cl, total cholesterol, triglycerides, CPK, albumin, Ca, P, total bilirubin, amylase) and Urinalysis (Glucose, protein, occult blood).

All data will be converted into SI units (except Cholinesterase, which will be reported as collected (in U/L)) listed for the safety set with abnormal values flagged. A listing of all patients in the safety set will be provided.

The change from baseline at Week 24 is provided for Hematology and Chemistry. For urinalysis, descriptive statistics is provided for baseline and Week 24.

Liver function tests

The metabolism of a drug can have an impact on the safety profile of the drug. To evaluate potential drug-induced liver injury, the patients with newly occurring or worsening abnormalities in liver function tests at any time post-baseline will be listed based on the following criteria:

Notable Liver events:

	Definition/ threshold
LIVER EVENTS	
 • ALT or AST $> 5 \times$ ULN • ALP $> 2 \times$ ULN (in the absence of known bone pathology) • TBL $> 2 \times$ ULN (in the absence of known Gilbert syndrome) • ALT or AST $> 3 \times$ ULN and INR > 1.5 • Potential Hy's Law cases (defined as ALT or AST $> 3 \times$ ULN and TBL $> 2 \times$ ULN [mainly conjugated fraction] without notable increase in ALP to $> 2 \times$ ULN) • Any clinical event of jaundice (or equivalent term) • ALT or AST $> 3 \times$ ULN accompanied by (general) malaise, fatigue, abdominal pain, nausea, or vomiting, or rash with eosinophilia • Any adverse event potentially indicative of a liver toxicity*

*These events cover the following: hepatic failure, fibrosis and cirrhosis, and other liver damage-related conditions; the non-infectious hepatitis; the benign, malignant and unspecified liver neoplasms

TBL: total bilirubin; ULN: upper limit of normal

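### The SAP's liver listing uses only the liver event criteria, so protocol-defined liver laboratory triggers (ALT/AST >3 to 5 × ULN, bilirubin >1.5 to 2 × ULN) are neither identified nor counted

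*Protocol*

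**What the plan says.** Protocol 7.3 sets out two categories for sites to consider, whether or not they are reported as adverse events. The first is "Liver laboratory triggers, which will require repeated assessments of the abnormal laboratory parameter". The second is "Liver events, which will require close observation, follow-up monitoring and completion of the standard base liver CRF pages". Table 14-1 in Appendix 2 gives the thresholds:

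- Triggers: ALT or AST above 3 and up to 5 × ULN; total bilirubin above 1.5 and up to 2 × ULN.
- Events: ALT or AST above 5 × ULN, ALP or total bilirubin above 2 × ULN (with stated exceptions), ALT or AST above 3 × ULN combined with INR above 1.5 or with listed symptoms, potential Hy's Law cases, jaundice, and adverse events suggesting liver toxicity.

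SAP 2.7.1 plans a listing to evaluate possible drug-induced liver injury. It covers patients whose "newly occurring or worsening abnormalities in liver function tests at any time post-baseline will be listed based on the following criteria". The table of criteria that follows carries over the event row of Table 14-1. The trigger row is absent and no reason is given.

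The same SAP section lists all laboratory data for the Safety Set, flags abnormal values, and summarises the chemistry change from baseline at Week 24. It plans no count of patients by multiple of ULN. For vital signs, by contrast, SAP 2.7.2 gives the number and percentage of patients with notable values and includes unscheduled and early-discontinuation visits.

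**The concern.** The protocol justifies its two-category process as a way to judge hepatotoxic potential more reliably. The SAP's liver listing keeps only the upper category. If that listing came out empty, a reader could take it to mean that no liver test abnormality worth naming occurred, although some patients might have crossed the protocol's own lower threshold. To find them, the reader would have to go through the general listing line by line and convert each value to a multiple of ULN.

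There is a smaller related problem. One event criterion needs an INR, which is not part of the scheduled laboratory panel. A zero against that criterion could mean that nobody met it or that nobody was tested, and the planned output would not show which.

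**Working it through.** The plan states no figure on this point, so there is none to reproduce. The check sets the two sets of definitions side by side and runs test profiles through both.

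**Inputs.** Let A be the higher of ALT and AST, and B total bilirubin, both in multiples of ULN.

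- Trigger (Protocol Table 14-1): 3 < A ≤ 5, or 1.5 < B ≤ 2.
- Listed under SAP 2.7.1: A > 5; or ALP > 2; or B > 2; or A > 3 with INR > 1.5; or a potential Hy's Law case; or jaundice; or A > 3 with a listed symptom; or a liver-type adverse event.

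**Held fixed.** ALP is 1 × ULN, with no jaundice and no liver-type adverse event.

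| A | B | Listed symptom | INR | Protocol trigger | In SAP liver listing |
|---|---|---|---|---|---|
| 2.5 or 3.0 | 1.0 | no | not measured | no | no |
| 2.5 or 3.0 | 1.8 | yes or no | either | yes | **no** |
| 3.01, 4 or 5 | 1.0 or 1.8 | no | not measured | yes | **no** |
| 3.01, 4 or 5 | 1.0 or 1.8 | yes | not measured | yes | yes |
| 3.01, 4 or 5 | 1.0 or 1.8 | no | > 1.5 | yes | yes |
| 3.01, 4 or 5 | 2.1 | no | not measured | yes | yes |
| 5.01 | 1.0 | no | not measured | no | yes |

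The bold rows are the gap: an ALT or AST in the trigger band with no symptom and no qualifying INR, and a bilirubin in the trigger band with ALT and AST at or below 3 × ULN. With the two trigger rows added to the SAP criteria, every profile marked as a trigger would be listed, whatever was known about INR.

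**Is such an ALT or AST value new?** Exclusion criterion 22 bars AST or ALT of 3 × ULN or above at screening. In an eligible patient, any later value above 3 × ULN is therefore new, for example a rise from 1 to 4.9 × ULN. The bilirubin exclusion is in mg/dL, not in multiples of ULN, so for bilirubin the comparison with baseline has to be made patient by patient.

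**Does the INR route close the gap?** The hematology panel in Protocol 6.5.3 is "Erythrocyte count, leukocyte count, hemoglobin, hematocrit, platelet count", and the chemistry panel contains no PT or INR. SAP 2.7.1 repeats both. Table 14-2 asks for PT/INR in follow-up of the more serious findings. Apart from the row defined by "> 3 × ULN and INR > 1.5", which already presupposes an INR result, those findings are liver events by another criterion. The row for an asymptomatic ALT or AST of 3 to 5 × ULN starts with "Repeat LFT within the next week", then close observation if confirmed and further liver tests within 1 to 4 weeks. It does not name INR. The planned tests therefore do not clearly bring any extra patient in through the INR criterion.

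**The case against.** The strongest reply is that Protocol 7.3 tells sites what to monitor and does not prescribe an analysis. Only liver events require dedicated CRF pages, and Protocol 9.6.2 describes adverse events and vital signs without any liver analysis. The SAP's listing thus already goes beyond the protocol. This stands, and it rules out reading the omission as a contradiction between SAP and protocol.

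A second reply is that nothing is lost from the report. The general listing flags abnormal values, the Week 24 chemistry summary includes minimum and maximum under the general rules of SAP 2.1, and a clinically significant laboratory value is an adverse event under Protocol 7.1. This also stands. It limits the harm but does not remove it: neither laboratory output states a multiple of ULN, and an asymptomatic value need not be judged clinically significant.

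Some stronger readings are tempting but not supported:

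- A reader might infer that the INR criterion will be empty because nobody is tested. The documents do not show this. INR can be obtained in follow-up or at the investigator's discretion, Protocol 7.3 provides an unscheduled local laboratory page for repeat tests, and the components of a liver function test are not spelled out.
- A reader might say that Hy's Law cases cannot be identified without conjugated bilirubin. Table 14-2, footnote a, defines them from ALT/AST, total bilirubin and ALP, all in the panel. Total bilirubin above 2 × ULN is also an event by itself, known Gilbert syndrome aside.
- Rash with eosinophilia does need a differential count, but it is one alternative among symptoms that otherwise need no laboratory test, so its effect is marginal.
- The single scheduled post-baseline sample is explicit in Table 6-1, and the SAP's wording also admits unscheduled values. This is not an error.

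**Conclusion.** The point holds as a reporting gap. SAP 2.7.1 leaves out one of the two liver categories that Protocol 7.3 and Table 14-1 define. A new ALT or AST above 3 and up to 5 × ULN that meets no event criterion, or an isolated bilirubin above 1.5 and up to 2 × ULN, is therefore absent from the one liver-specific output and is not counted elsewhere by grade.

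The size in patients is unknown, because the documents give no expected frequency of such values. The study is single-arm with about 120 patients, uses a marketed drug and plans no inference on liver safety, so the consequence is confined to how the liver profile is described. It does not touch the primary analysis.

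The conclusion assumes that the SAP criteria are applied as written and that the general listing flags values as abnormal without grading them. It does not depend on INR being unavailable, since leaving out the trigger row is enough to create the gap.

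**What to change.** In SAP 2.7.1:

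1. Add the two trigger rows of Protocol Table 14-1 to the criteria.
2. Tabulate the number and percentage of Safety Set patients meeting each trigger and each event, classified on the worst post-baseline value from scheduled, discontinuation and unscheduled samples, and list those patients. SAP 2.7.2 already does this for notable vital signs.
3. Beside the criterion that combines ALT or AST above 3 × ULN with INR above 1.5, print the number of patients who had an INR result, so that an untested patient is not read as a negative one.

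The cost is a few lines of SAP text, one small table and one listing. The event criteria already work in multiples of ULN, so the trigger rows need no data item that the SAP does not already use. No test, visit or clinical rule changes.

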## **7.4 Renal safety monitoring**

The following two categories of abnormal renal laboratory values have to be considered during the course of the study:

- Serum event:
  - Confirmed (after  $\geq 24\text{h}$ ) increase in serum creatinine of  $\geq 25\%$  compared to baseline during normal hydration status
- Urine event
  - New onset ( $\geq 1+$ ) proteinuria; confirmed by doubling in the urinary albumin-creatinine ratio (ACR) or urinary protein-creatinine ratio (PCR) (if applicable)
  - New onset ( $\geq 1+$ ), hematuria or glycosuria

Every renal laboratory trigger or renal event as defined in [Table 15-1 in Appendix 3](#) should be followed up by the investigator or designated personnel at the trial site as summarized in [Appendix 3](#).

## **7.5 Reporting of study treatment errors including misuse/abuse**

Not applicable

## **7.6 Pregnancy reporting**

To ensure patient safety, each pregnancy occurring after signing the informed consent must be reported to Novartis within 24 hours of learning of its occurrence. The pregnancy should be followed up to determine outcome, including spontaneous or voluntary termination, details of the birth, and the presence or absence of any birth defects, congenital abnormalities, or maternal and/or newborn complications.

Pregnancy must be recorded on the Pharmacovigilance Pregnancy Form and reported by the investigator to the local Novartis Drug Safety and Epidemiology Department. Pregnancy follow-up should be recorded on the same form and should include an assessment of the possible relationship to the drug.

Any SAE experienced during the pregnancy and unrelated to the pregnancy must be reported on a SAE form.

Pregnancy outcomes should be collected for the female partners of any males who took the drug in this study. Consent to report information regarding these pregnancy outcomes should be obtained from the female partner.

## 8 Data review and database management

### 8.1 Site monitoring

Before study initiation, at a site initiation visit, a CRO working on behalf of Novartis will review the protocol and eCRFs with the investigators and their staff. During the study, the field monitor will visit the site regularly to check the completeness of patient records, the accuracy of entries on the eCRFs, the adherence to the protocol, to Good Clinical Practice (GCP) and Good Post-marketing Study Practice (GPSP), the progress of enrollment. Key study personnel must be available to assist the field monitor during these visits.

The investigator must maintain source documents for each patient in the study, consisting of case and visit notes (hospital or clinic medical records) containing demographic and medical information, laboratory data, electrocardiograms, and the results of any other tests or assessments. All information on eCRFs must be traceable to these source documents in the patient's file. *[Data not requiring a separate written record will be defined before study start and will be recorded directly on the CRFs.]* The investigator must also keep the original informed consent form signed by the patient (a signed copy is given to the patient).

The investigator must give the monitor access to all relevant source documents to confirm their consistency with the eCRF entries. Novartis monitoring standards require full verification for the presence of informed consent, adherence to the inclusion/exclusion criteria, documentation of SAEs, and the recording of data that will be used for all primary and safety variables. Additional checks of the consistency of the source data with the eCRFs are performed according to the study-specific monitoring plan. No information in source documents about the identity of the patients will be disclosed.

